3. DATA NOT FROM CRFS

The Optum™ SF-12v2 assessment is an online questionnaire used to measure physical and mental health. Composite scores for these two measures are calculated by Optum, stored on Optum servers, and can be extracted as needed. Data for the continuous performance task included in the EDC does not reflect all the raw data available for analysis. Raw data for this online assessment is captured and stored on Amazon servers and can be extracted for analysis.

- SF-12 Physical Composite Score
- SF-12 Mental Composite Score
- Continuous Performance Task

- Posner Task
- Spatial Working Memory
- Greyscales

4. CALCULATION OF DOMAIN COMPOSITE SCORES

The composite is composed of the individual measures described in section 1 (above), combined as follows:

- i. For each included variable convert the distribution of raw scores in the ITT population at baseline to z-scores (with a mean of 0 and a standard deviation of 1). Note that the raw score distribution may be non-normal (with skew or kurtosis) and the goal of this step is to transform that distribution into a normal distribution.
- ii. Calculate the composite score at V_1 , V_2 , and V_3 for each participant based on the baseline data set.

Five a priori domain specific composites are defined as follows and constructed as above
Spatial Cognition: Greyscales Task (raw scores), Spatial Working Memory Task (raw scores)

Cognitive Performance: DKEFS Verbal Fluency (Letter Fluency, raw scores; Category Fluency total, raw scores; Category Switching total, raw scores; Category Switching, switching Accuracy total, raw scores), WAIS-IV Digit Span total (sum of forward, backward, sequencing raw scores), WAIS-IV Digit Span (Forward total, raw scores; Backward total, raw scores; Sequencing total, raw scores), Continuous Performance Task (raw scores)

Functional Ability: Catherine Bergego Scale total (raw score), Barthel Index total (raw score)

Quality of Life: SF-12 Physical Composite Score, SF-12 Mental Composite Score

Quality of Sleep: Pittsburgh Sleep Quality Index total (sum of component scores), Pittsburgh Sleep Quality Index Sleep Efficiency (raw score), Component scores

ANALYSIS POPULATIONS

There are four *a priori* defined analysis populations, including a primary analysis population (i), three secondary analysis populations designed to compare effect sizes: populations with no missing data (ii), populations who completed all training visits (iii), and populations that demonstrated a bias in spatial attention at baseline (iv).

- iii. *Intent to Treat (ITT) population:* This is the *a priori* primary analysis population, defined as including all randomized participants who completed the training set-up visit
- iv. *Intent to Treat (ITT) Fully-Evaluable (FE) population:* This is a secondary analysis population, defined as including all members of the ITT population that complete a post-intervention or V2 visit (the ITT-FEV2 population), or all members of the ITT

population that completed a V3 or delayed follow up visit (the ITT-FEV3 population). Note that a participant may complete a specific visit but have missing data for a test in which case the participant is in the overall FE population but does not contribute data to the FE population for that visit, e.g., the number of evaluable cases for a specific test on a specific visit may be smaller than the FE population for that visit because of missing data.

- v. *Intent to Treat (ITT) Fully-Trained (FT) population:* This is a secondary analysis population, defined as including all members of the ITT-FE population who complete a target number of training visits (32 visits). Note that the FT populations are strict subsets of the FE populations; a person who completes the target number of training visits but does not complete the evaluation visit is not a member of the FT population.
- vi. *Intent to Treat (ITT) Spatial-Bias (SB) population:* This is a secondary analysis population, defined as including all members of the ITT population who demonstrate a bias in spatial attention that is numerically greater on the ipsilesional side of space on the primary outcome measure (Posner cueing task – field bias).

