1. GENERAL STATISTICAL PLAN

The data analysis plan *a priori* defines a primary intent-to-treat (ITT) population, a set of secondary evaluation populations, a primary outcome measure, a set of secondary outcome measures, a single primary evaluation time point, a secondary evaluation time point, a primary statistical analysis methodology, a criterion for statistical significance, and guidance for interpretation of results.

The **primary ITT population** is defined as all participants who complete a training set-up visit. Note that this includes all randomized participants except those who drop/withdraw post-randomization and pre-setup visit.

The **primary outcome measure**, per determination of an independent external review committee comprised of experts in the diagnosis and evaluation of the trial target population (i.e., individuals with hemispatial neglect following acquired brain injury), is the Posner cueing task; a spatial attention measure that captures the visual *Field Bias* score (average reaction time to Left trials – average reaction time to Right trials), as reported here:

Rengachary, J., d'Avossa, G., Sapir, A., Shulman, G. L., & Corbetta, M. (2009). Is the posner reaction time test more accurate than clinical tests in detecting left neglect in acute and chronic stroke?. *Archives of physical medicine and rehabilitation*, 90(12), 2081-2088.

To capture a valid assessment of participants' performance in the Posner cueing task (*Field Bias* score) independent of criterion shifts or speed-accuracy trade-offs [Lange-Malecki and Treue, 2012; Spence et al., 2001; Teufel et al., 2010], we will employ an inverse efficiency scoring approach (IES; Townsend and Ashby, 1983) to account for potential differences in accuracy across Left and Right trial types (e.g., Valid and Invalidly cued trials). Mean reaction times (RTs) will be divided by the proportion of correct trials responded to in each specific condition.

The **secondary outcome measures** will evaluate training exercise-based progress, as well as performance in several measures identified by domain, including: spatial attention, spatial cognition, cognitive performance, functional ability, quality of life, and quality of sleep.

Spatial Cognition

- Greyscales Task (raw scores)
- Posner Cueing Task (raw scores)
- Spatial Working Memory Task (raw scores)

Cognitive Performance

- DKEFS Verbal Fluency Letter Fluency (raw scores)
- DKEFS Verbal Fluency Category Fluency total (raw score)

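### The Section 4 composites enter Digit Span and PSQI totals beside their own parts, depart from the Section 1 lists in two of five domains, and state no direction rule (minor)

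*SAP*

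**What the plan says.** Section 4 of the SAP opens with a rule for what goes into a composite: "The composite is composed of the individual measures described in section 1 (above), combined as follows". Step i converts each raw score to a z-score on the baseline ITT distribution and adds that "the goal of this step is to transform that distribution into a normal distribution". Step ii reads "Calculate the composite score at V_1 , V_2 , and V_3 for each participant based on the baseline data set". Neither step mentions reversing the sign of any item, weights, or whether a sum or a mean is taken. The item lists then follow: "Five a priori domain specific composites are defined as follows and constructed as above".

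Three of those lists matter here.

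- **Spatial Cognition.** Section 4 has "Spatial Cognition: Greyscales Task (raw scores), Spatial Working Memory Task (raw scores"). Under the same domain, Section 1 also lists "Posner Cueing Task (raw scores").
- **Cognitive Performance.** Among nine entries are "WAIS-IV Digit Span total (sum of forward, backward, sequencing raw scores), WAIS-IV Digit Span (Forward total, raw scores; Backward total, raw scores"), with the sequencing score after them.
- **Quality of Sleep.** Section 4 has "Quality of Sleep: Pittsburgh Sleep Quality Index total (sum of component scores), Pittsburgh Sleep Quality Index Sleep Efficiency (raw score), Component scores". Section 1 lists only the PSQI total and Sleep Efficiency.

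Section 2 defines PSQI total as the sum of seven components, one of which is sleep efficiency. It derives efficiency in two steps, first a percentage and then a 0–3 recode.

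**The concern.** A composite is only as clear as its item list, signs and weights. Here the section that defines the composites breaks its own membership rule in two domains. It gives two instruments extra weight by entering a total and its parts together, and it offers no reason for doing so. It also does not say which way each raw score points before the z-scores are combined. An item that runs opposite to the others, and is not reversed, offsets real change in its domain.

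At stake is the meaning of the composites used in the exploratory analyses of Section 1. Those analyses correlate neglect severity or subtype with gain scores on composites, and training progress with composite scores. The primary outcome is not a composite.

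**Working it through.** The SAP gives no figure on this point, so there is none to reproduce. The check compares the lists and then works through the weights and directions.

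**1. Lists compared as sets (Section 1 against Section 4)**

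| Domain | Section 1 | Section 4 | Difference |
|---|---|---|---|
| Spatial Cognition | 3 | 2 | Posner only in Section 1 |
| Cognitive Performance | 9 | 9 | none |
| Functional Ability | 2 | 2 | none |
| Quality of Life | 2 | 2 | none |
| Quality of Sleep | 2 | 2 plus component scores | component scores only in Section 4 |

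Two of five domains differ. Under equal weights, Posner carries 1/3 of Spatial Cognition on the Section 1 list and nothing on the Section 4 list. The other two items go from 1/3 to 1/2 each.

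**2. Digit Span weight (equal weights assumed)**

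- As listed, total plus three parts among nine entries: 4/9 = 44%.
- Total only, three entries removed: 1/6 = 17%.
- Parts only, one entry removed: 3/8 = 38%.

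If the three parts have equal SDs and a common correlation r (both assumed), the standardised total is (F + B + S)/√(3 + 6r). Each part then carries a weight of 1 + 1/√(3 + 6r) relative to any other single entry. This is 1.46 at r = 0.3, 1.41 at r = 0.5 and 1.37 at r = 0.7.

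The same four scores stand in Section 1. As separate outcomes there, the overlap does no harm. It becomes double weighting only in a composite.

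**3. PSQI**

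Section 2 sums seven components to the total. Section 4 enters that total and then component scores, a term that it does not define. It follows two PSQI entries, and Section 2 uses the same term for the PSQI components, so these are very probably meant. On that reading the structure is the same as for Digit Span.

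**4. Direction of Sleep Efficiency**

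Applying the Section 2 recode:

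| Efficiency (%) | 60 | 70 | 80 | 90 |
|---|---|---|---|---|
| Component | 3 | 2 | 1 | 0 |

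The percentage falls as its component rises, so it runs opposite to that component and to the total that contains it. There are two readings of the raw score:

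- *Percentage.* It needs reversing before it is combined, and Section 4 does not say so.
- *0–3 recode.* There is no sign conflict, but the efficiency component is then entered as its own item, inside the total and, if all components are entered, once more among them.

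The text does not say which is meant, and each reading leaves something to correct.

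**5. Normality**

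With z = (x − m)/s, where m and s are the baseline mean and SD, the transformation is linear. Location and scale change; skewness and kurtosis do not. A skewed raw score gives an equally skewed z-score, so step i cannot reach its stated aim.

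**The case against.** The best defence is that Section 4 gives closed lists, so an analyst knows which variables to use, and that step i speaks of included variables, which allows a subset of Section 1. Section 1 also calls the Posner task a measure of spatial attention and names that domain apart from spatial cognition. Leaving the primary outcome out of a secondary composite would be a sensible choice. This stands in part: the omission may well be deliberate. But the opening rule of Section 4 points to the Section 1 measures, and nothing says that Posner was dropped on purpose. The defence does not cover the sleep list, which adds items instead of selecting them.

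On Digit Span, it can be said that the weights are a matter of preference and that parts-only still gives 38%. That is fair as to size. It does not explain why a sum should be entered beside its own terms.

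On direction, a reader might infer that the composites are certainly mis-signed and that the sleep composite would lose a sizeable share of any benefit. The document does not support this. The only conflict that it can show depends on the raw score being the percentage. The directions of the two Functional Ability scales are not given, so nothing can be claimed there. Nor can a loss be calculated by letting PSQI total shift and correlate like a single component, because it is their sum. For these reasons no effect-size figure is given for sleep.

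**Conclusion.** The point holds and is minor. Three parts rest on the text alone: the lists differ in two of five domains, Digit Span total is entered beside the three scores that it sums, and z-scoring is given an aim that it cannot meet. The PSQI overlap rests on the natural reading of component scores. The sign conflict is conditional on the meaning of the Sleep Efficiency raw score.

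The size that can be stated is the Digit Span share: 44% as listed, against 17% or 38%, assuming equal weights.

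The reach is limited. The composite analyses named in Section 1 are exploratory and Bonferroni-corrected, and individual measures are analysed alongside. No analysis names the sleep composite. Section 1 refers to executive and attention composites, which are not Section 4 domains. The Digit Span weights therefore bear on those analyses only if executive performance means Cognitive Performance. A reader might suppose that the main result of the trial is affected; it is not, because the Field Bias analysis uses no composite.

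**What to change.** Edit Section 4 as follows.

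- For Digit Span and for PSQI, enter either the total or its parts, not both.
- Sign every item so that higher means better before combining.
- State whether Sleep Efficiency is the percentage or the 0–3 recode.
- Make the Section 1 and Section 4 lists agree, and say whether leaving Posner out of Spatial Cognition is deliberate.
- Delete the aim of reaching a normal distribution from step i.

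The cost is SAP wording and edits to the scoring scripts, with no new data. Keeping only totals or only parts takes some detail out of the composites, but the individual measures are still analysed separately.

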- DKEFS Verbal Fluency Category Switching total (raw score)
- DKEFS Verbal Fluency Category Switching accuracy total (raw score)
- WAIS-IV Digit Span total (sum of forward, backward, sequencing raw scores)
- WAIS-IV Digit Span Forward total (raw scores)
- WAIS-IV Digit Span Backward total (raw scores)

- WAIS-IV Digit Span Sequencing total (raw scores)
- Continuous Performance Task (raw scores)

Functional Ability

- Catherine Bergego Scale total (raw score)
- Barthel Index total (raw score)

Quality of Life

- SF-12 Physical Composite Score
- SF-12 Mental Composite Score

Quality of Sleep

- Pittsburgh Sleep Quality Index total (sum of component scores)
- Pittsburgh Sleep Quality Index Sleep Efficiency (raw score)

The **primary analysis time point** is V2, the post-training assessment. The **secondary analysis time point** is V3, the follow-up assessment.

The **primary statistical analysis methodology** is a linear mixed-effects model approach. We will first compare treatment and active control groups in the ITT population to determine if any differences in baseline demographic, characterization, outcomes variables, or total program use time remain after the randomization process. Any such factors that show trend level significant differences ($p < 0.1$) will be noted and used as covariates in the linear mixed model analysis. We will examine the data from each outcome measure using a linear mixed model with group and time as fixed factors, site as a random factor, and co-variates as necessary from the baseline analysis. Missing data will be handled with an iterative maximum likelihood procedure to optimally estimate model parameters. The key value for significance will be the group-by-time interaction factor for the model. This modeling will be conducted with a Type I error set at 0.05 for each model.

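### The Fully-Trained set is named intent-to-treat but is selected on two post-randomisation events, so its effect size is not a randomised comparison and its change contrast is open to regression to the mean

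*SAP*

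**What the plan says.** The Analysis Populations list (SAP, after section 4) has one primary set and "three secondary analysis populations designed to compare effect sizes". The primary set is "defined as including all randomized participants who completed the training set-up visit". Item v, the "Intent to Treat (ITT) Fully-Trained (FT) population", takes members of the Fully-Evaluable set who complete 32 training visits. It then makes the second condition explicit: "a person who completes the target number of training visits but does not complete the evaluation visit is not a member of the FT population". The introductory sentence of the same list mentions only completion of all training visits, so item v is narrower than that description.

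Section 1 sets out the model: group and time as fixed factors, site as a random factor, and the group-by-time interaction as the key test. It gives one rule for covariates: "We will first compare treatment and active control groups in the ITT population". Factors that differ at p < 0.1 "will be noted and used as covariates in the linear mixed model analysis". For incomplete data it says: "Missing data will be handled with an iterative maximum likelihood procedure". It does not say how covariates are to be chosen for the Fully-Trained set, and it gives no caution on reading that set's effect size.

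**The concern.** Completing 32 visits and returning for assessment both happen after randomisation. The arms use an experimental program and an active control, so those who finish one need not resemble those who finish the other. The contrast within the set therefore mixes any effect of full training with who remains in each arm.

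The group-by-time term compares change from baseline. If one arm's completers are selected on a high baseline Field Bias, their scores tend to fall towards the mean with no treatment effect, and the contrast records this as benefit. The result is then set beside the ITT effect size under a name that suggests the protection of randomisation. A difference between the two figures could be read as the benefit of full training when it may reflect selection.

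**Working it through.** **Plan's own figure.** There is none. The SAP gives no sample size, completion rate, SD or baseline-to-V2 correlation for this point. All inputs below are assumptions, and the true treatment effect is set to 0.

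**Model.** Baseline B is standard normal. V2 = ρB + √(1−ρ²)e, with ρ = 0.5 or 0.7. Change = V2 − B, with SD √(2(1−ρ)). The probability of being in the set is expit(a + sB). With m_T and m_C the mean baseline among completers in each arm:

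contrast in SD of change = −k(m_T − m_C), where k = √((1−ρ)/2), which is 0.500 at ρ = 0.5 and 0.387 at ρ = 0.7.

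**Selection in the treatment arm only (m_C = 0).**

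| s | a | completion | m_T | size, ρ = 0.5 | size, ρ = 0.7 |
|---|---|---|---|---|---|
| 0.5 | 0.4 | 59% | 0.192 | 0.096 | 0.074 |
| 0.5 | 1.4 | 79% | 0.100 | 0.050 | 0.039 |
| 1.0 | 0.4 | 58% | 0.347 | 0.173 | 0.134 |
| 1.0 | 1.4 | 76% | 0.203 | 0.101 | 0.078 |

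The strongest case is 0.500 × 0.347 = 0.173. Simulation with 2,000,000 participants per setting gives the same range, 0.039 to 0.173. The direction favours treatment if participants with larger baseline bias stay in the treatment arm, and reverses if the milder ones stay.

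**Same slope in both arms, control completion higher.** With control intercept 1.9, control completion is 86% at s = 0.5 (m_C = 0.068) and 83% at s = 1.0 (m_C = 0.147). The smallest value is 0.387 × (0.100 − 0.068) ≈ 0.01. The largest is 0.500 × (0.347 − 0.147) = 0.10.

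**Identical selection in both arms.** m_T = m_C, so the bias is 0.

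**Effect on a test.** With 50 randomised per arm, 85% control completion unrelated to baseline and the strongest one-arm selection, a nominal 0.05 test of change rejects about 11% of the time (ρ = 0.5) or about 8.5% (ρ = 0.7). At the weakest setting the rate is about 5.5%.

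**What adjustment does.** In the same model, adjusting V2 for baseline brings the bias within 0.002 of 0. The form of adjustment matters. A baseline covariate entered only as a main effect adds the same amount to a participant's baseline and V2 rows, so with both visits present it cancels from the difference in change. In one simulated data set the group-by-time estimate was −0.193 with or without such a covariate, against −0.024 with covariate-by-time terms or ANCOVA.

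**Selection on prognosis that is not measured.** If completion follows a latent score correlated r with change itself, the bias is r_T φ(z_T)/p_T − r_C φ(z_C)/p_C, where z is the normal cut-off for completion rate p. At 60% against 80% with r = 0.5 in both arms: 0.5 × (0.644 − 0.350) = 0.147. With the correlation in the treatment arm only: 0.5 × 0.644 = 0.322. At 80% in both arms with equal r: 0. Baseline adjustment does not remove this component. Under milder assumptions (correlation with change 0.2 to 0.4, completion 58% to 67% against 81%) it is 0.02 to 0.07 SD.

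**The case against.** The set is explicitly secondary, no claim or decision rule rests on it, and a completer set reported beside ITT is common practice. The SAP uses ITT as a prefix for every subset and states both membership conditions openly. All of this stands, and it limits the point to a secondary effect size and its label. The Fully-Evaluable set shares the attendance condition; the Fully-Trained set adds selection on training.

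A reader might infer more than the document supports:

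- **That the Fully-Trained result will favour treatment.** Without completion rates, neither size nor direction is known, and 0 is possible.
- **That imbalance in this set is barred from examination.** Section 1 describes one screen, in the ITT set, and is silent on the others. Silence is not a prohibition. Repeating that screen and entering the flagged factors as main effects would not solve the problem in any case.
- **That the ITT set is a clean randomised benchmark.** It leaves out those who withdraw before the set-up visit, and the covariate screen includes total program use time, which arises after randomisation.
- **That dropping the attendance condition and relying on maximum likelihood would repair the set.** The stated model names only site as a random factor. Without a within-participant correlation, participants lacking V2 shift the baseline mean and have no link to V2. If V2 attendance in the treatment arm follows s = 1.0 and a = 1.4, the absolute bias becomes ρm_T/√(2(1−ρ)). At ρ = 0.5 this is 0.5 × 0.203/1.000 ≈ 0.10, unchanged. At ρ = 0.7 it is 0.7 × 0.203/0.775 ≈ 0.18, against 0.08 among those with both visits. Selection on 32 visits would also remain.

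**Conclusion.** The point holds as a matter of definition: a set chosen on two post-randomisation events should not carry an intent-to-treat name, and its contrast is not protected by randomisation. The group-by-time term does not remove regression to the mean when completion depends differently on baseline in the two arms.

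Under assumed baseline-driven selection and no treatment effect, the bias runs from 0 to about 0.17 SD of change. The upper end needs selection in one arm only. The 0.17 is not a ceiling if completion also tracks unmeasured prognosis. The primary ITT conclusion is unaffected, so this should be corrected but does not threaten the trial's main claim.

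**What to change.** 1. Rename the set fully trained (per-protocol). Report completion and baseline characteristics by arm beside its effect size, and state that the contrast is descriptive and not a randomised comparison.
2. For this set, estimate the effect with the post-training score adjusted for baseline Field Bias (ANCOVA), or with a baseline-by-time term in the mixed model. Add Mesulam misses in the same form if numbers allow. Do not rely on a main-effect covariate in the section 1 model.
3. Keep the evaluation-visit condition unless the model includes a within-participant correlation, and make the introductory sentence of Analysis Populations agree with item v.

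The cost is SAP wording, one adjusted secondary model on planned data, and a less favourable label. Bias from unmeasured prognosis remains, which is why the result should still be called descriptive.
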